The questionnaire that will be used is the Cystic Fibrosis Questionnaire-Revised (CFQ-R) Respiratory domain (44). The CFQ-R is a disease-specific instrument that measures health-related quality of life for adolescents and adults with CF with a developmentally appropriate version for children. The CFQ-R is a reliable and valid measure of quality of life for individuals with CF and is frequently used in clinical trials to assess the effects of new therapies (45). In addition, subjects will also be asked to complete the CF Respiratory Symptom Diary (CFRSD) on day 0, day 7, day 14 and at the 1 month follow up visit(46). The Chronic Respiratory Infection Symptom Score will be applied to the CFRSD to calculate a severity score from 0-100 (100 being most severe). The CRISS score has been previously shown to be a responsive measure of steroid treatment effect in CF pulmonary exacerbations(47).

iv)The length of hospitalization and duration of IV antibiotic treatment in each treatment arm.

Length of hospitalization (number of days in hospital) and duration of IV antibiotic treatment are clinically relevant and patient-meaningful outcomes that will be calculated for each patient and compared between treatment groups.

v) The time to subsequent PEx in each treatment arm.

Based on our previous study, we know that the time between exacerbations is one of the most important determinants of overall lung function decline in an individual with CF (6). Time to subsequent pulmonary exacerbation will be calculated from the last day of IV antibiotic therapy of the randomized exacerbation to the first day of re-starting IV antibiotic treatment for a new pulmonary exacerbation (minimum 21 days between events). We will compare the average (or median if data not normally distributed) duration between treatment groups. We will follow up patients for subsequent exacerbations for 1 year following their randomized exacerbation.

vi) The number of adverse events and withdrawals from study recorded in each treatment arm.

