When target sample size is reached, the study statistician (who will not be involved in the conduct of the study) will unblind the treatment allocation (identify who is in group A vs B but not identify the groups themselves as active drug or placebo) and estimate the treatment effect between the two groups based on the primary outcome (intention-to-treat). If there is a statistically significant treatment effect ($p<0.05$), the study statistician will do the following statistical analyses. For the primary outcome we will compare the proportion of randomized patients that responded at day 14 of therapy in the placebo arm compared with the treatment arm using a two sample test for proportions. We will perform intent-to-treat analysis according to the treatment arm subjects were randomized to. We will also perform a per-protocol analysis based on subjects who completed the 7 days of prednisone or placebo as per protocol. The same analysis will be performed for the proportion responding to therapy at 1 month. Logistic regression analysis will then be performed to adjust for potential confounders, such as age, gender, *Pseudomonas aeruginosa* or methicillin-resistant *Staphylococcus aureus* (MRSA) infection and lower FEV₁, as these factors have been associated with failure to recover lung function after an exacerbation (3, 25). For the additional secondary outcomes, absolute change in pulmonary function tests, length of hospitalizations and change in sputum measurements,

we will use parametric (t-test), or non-parametric (Mann-Whitney) two sample comparison test. Linear regression analysis will be then performed to adjust for potential confounders, as listed above. Time to subsequent exacerbation will be compared using a Cox proportional hazard model. Potential confounders will be adjusted for in the Cox-proportional hazard model. All secondary outcomes will be analyzed both as intention-to-treat and per-protocol. All outcomes will be obtained for all subjects irrespective of whether they completed the study per protocol. In the case of missing data, we will perform the analysis on complete (complete case analysis). To determine whether diabetic patients have a different response compared to non-diabetic patients, we will perform a sensitivity analysis comparing return to baseline lung function in diabetics vs non-diabetics according to treatment group.

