height using the NIH guidelines(56)) and will monitor for these adverse events (see below-Safety Monitoring Plan). In addition, all untoward medical occurrences, whether or not deemed causally related to study participation, will be recorded and site investigators will be asked to assess both severity and whether or not the adverse event was related to study participation. We will use the following grading scale to assess adverse events:

Adverse Event Category	Description
Mild	transient event, no treatment change, e.g. glucosuria
Moderate	treatment discontinued e.g. severe/sustained hypertension or hyperglycemia
Severe	severe: death, unexpected hospitalization

Given that subjects will be randomized at the time of hospitalization for a pulmonary exacerbation, we will monitor the time to subsequent exacerbation. If we observe a shorter time to subsequent exacerbation in one of the treatment arms, this will be reported to the DSMB.

Reporting of AEs

All adverse events will be recorded by the research coordinator and reported to the study site investigator as well as the PI ([name]), who will oversee close and continuous monitoring for safety concerns throughout the trial. All serious adverse events will be reported to Health Canada, based on the Health Canada Guidance: Adverse Drug Reactions (ADRs) Reporting Criteria. All serious and unexpected adverse events will also be reported to the REB at each study site as well the REB at the Hospital for Sick Children (as study sponsor) within 48 hours of their occurrence. Adverse events will also be reported to the Data Safety Monitoring Board (DSMB) (see below) in the form of regular reports submitted every 6 months. Serious adverse events will be reported to the DSMB within 48 hours.

Safety Monitoring Plan

Hospitalized subjects will be monitored on day 7, day 10 (+/- 2 days) and on day 14 with urine dip glucose measurements while on prednisone (or placebo). If the urine glucose is > 2+, a serum glucose measurement will be performed. All the information will be provided to the treating physicians; they can decide at any time to withdraw their patient and request unblinding of the treatment allocation. To unblind a subject, the research coordinator or physician will call the PI ([name]) at [contact] [name] or page [contact]

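### Secondary outcome v), time to next exacerbation: Section E compares an average or median duration, Section G names a Cox model, and no rule says how patients without a new exacerbation by 1 year are counted

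*Combined protocol and SAP*

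**What the plan says.** Section E, secondary outcome v), measures time from the last day of IV antibiotics for the randomised exacerbation "to the first day of re-starting IV antibiotic treatment for a new pulmonary exacerbation (minimum 21 days between events"). It then gives the comparison: "We will compare the average (or median if data not normally distributed) duration between treatment groups". Follow-up is limited: "We will follow up patients for subsequent exacerbations for 1 year following their randomized exacerbation".

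Section G gives a different comparison for the same outcome: "Time to subsequent exacerbation will be compared using a Cox proportional hazard model", with adjustment for potential confounders. For pulmonary function change, length of hospitalisation and sputum change it says "we will use parametric (t-test), or non-parametric (Mann-Whitney) two sample comparison test". Time to exacerbation is not in that list.

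Two general statements in Section G lie close to the question. One is "All outcomes will be obtained for all subjects irrespective of whether they completed the study per protocol". The other is "In the case of missing data, we will perform the analysis on complete (complete case analysis"). Neither mentions patients who complete follow-up without an event.

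Appendix 1.2 uses the same outcome for safety: "If we observe a shorter time to subsequent exacerbation in one of the treatment arms, this will be reported to the DSMB". It gives no method.

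**The concern.** The duration in Section E is known only for patients who restart IV antibiotics within the year. For the rest, all that is known is that the time exceeds their follow-up. An average or median of durations therefore needs a rule for these patients, and the documents give none. Section G's Cox model would keep them as censored observations, but nothing says that Section G overrides the comparison stated in Section E.

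Suppose Section E were followed and event-free patients were treated as having no value. The comparison would then be confined to patients who had an exacerbation. That subgroup is formed after randomisation and is itself affected by treatment: the better an arm does, the more of its patients drop out of the average. A real benefit would be understated, and the published average could disagree with the Cox result.

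Two related details are open. The 1-year follow-up is counted from the randomised exacerbation, while the duration starts on the last IV day. Section G also begins the analysis when the target sample size is reached, without saying whether this outcome waits for the last patient's year to end.

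**Working it through.** **Plan's own figure.** The documents give no event rate, hazard ratio or power for this outcome. The only sample size is for the primary outcome (30% v 60%, 80% power, 5% level, taken as two-sided). With pooled variance:

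n per arm = [1.960 × √(2 × 0.45 × 0.55) + 0.842 × √(0.30 × 0.70 + 0.60 × 0.40)]² / 0.30² = (1.379 + 0.565)² / 0.09 ≈ 42, or 84 in total, as stated in Section F.

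It is used below only for the arm size.

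**Assumptions, not in the documents.** Exponential times, 42 per arm, everyone followed for 365 days. The placebo 1-year event probability p₀ is 50%, 65% or 80%, and the hazard ratio (HR) is 0.6, with 0.5 to 0.8 as the range. The Background does report that 38% of all US CF patients seen in care centres in 2007 had at least one IV-treated exacerbation. That is not a rate for patients who have just failed to recover by day 7 of an exacerbation, so it is used only as a low-end check.

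**Formulas** (λ per year):
- λ₀ = −ln(1 − p₀); λ₁ = HR × λ₀; p₁ = 1 − e^(−λ₁)
- Event-free patients per arm = 42 × e^(−λ)
- Mean exacerbation-free days to 1 year = 365 × (1 − e^(−λ)) / λ
- Mean duration among patients with an event = 365 × [1/λ − e^(−λ) / (1 − e^(−λ))]

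**Worked case, p₀ = 65%, HR 0.6.** λ₀ = 1.050, λ₁ = 0.630, p₁ = 0.467.
- Exacerbation-free days: 226.0 v 270.8, difference 44.8.
- Events only: 365 × (0.953 − 0.538) = 151.1 v 365 × (1.588 − 1.140) = 163.5, difference 12.3.
- Share shown: 12.3 / 44.8 = 27%.

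**All three rates, HR 0.6** (placebo v prednisone):

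| | p₀ 50% | p₀ 65% | p₀ 80% |
|---|---|---|---|
| Event-free patients | 21.0 v 27.7 | 14.7 v 22.4 | 8.4 v 16.0 |
| True difference, days | 35.3 | 44.8 | 52.6 |
| Event-only difference, days | 8.3 | 12.3 | 18.0 |
| Power, log-rank (unadjusted Cox) | 33% | 41% | 51% |
| Power, event-only t-test | 6% | 7% | 11% |
| Power, event-free entered at 365 days, t-test | 27% | 35% | 45% |
| Same, Mann-Whitney | 30.9% | 38.5% | 45.6% |

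Powers are from 3,000 simulations per case. As a check, the Schoenfeld formula, Φ(|ln HR| × √events / 2 − 1.96), with 35.3, 46.9 and 59.6 expected events gives 33%, 42% and 51% for log-rank.

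**Share of the true difference shown by the event-only average, HR 0.5 to 0.8:**

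| p₀ | 38% | 50% | 65% | 80% | 90% | 95% |
|---|---|---|---|---|---|---|
| Share | 21-22% | 23-25% | 27-29% | 33-37% | 41-48% | 49-58% |

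**No true effect (HR 1.0).** Rejection rates are 4.9-5.1% for log-rank and 5.3-5.8% for the event-only t-test, so false-positive error stays near 5%.

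**Medians.** At HR 0.6 the true prednisone medians are 608, 402 and 262 days. Two of the three lie beyond 1 year, so a Kaplan-Meier median would often be unavailable as a substitute.

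**The case against.** The strongest reply is that Section G is the analysis section, it names a model built for censored times, and it leaves this outcome off the t-test and Mann-Whitney list. The 1-year window then implies censoring at 1 year, and the Section E sentence may be a leftover summary. Much of this stands: if Section G is followed, the loss shown above does not occur. What remains is that Section E says the arms will be compared on that duration, and neither the precedence nor the censoring is written down.

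A reader might infer that the plan drops event-free patients. The documents do not say so. The complete-case rule is for missing data, and a patient followed for a year without an event has been observed. The statement that outcomes are obtained for all subjects concerns those who did not complete the study per protocol, so it does not settle how event-free patients are counted. Dropping them requires setting the Cox model aside and stretching the complete-case rule.

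It is also fair that Section E can be followed at little cost. Entering 365 days for event-free patients gives 27-45% power by t-test, against 33-51% for log-rank, though it requires a full year on every patient.

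Finally, the DSMB sentence in Appendix 1.2 is a reporting trigger and not a planned test, so specifying a method there is optional.

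**Conclusion.** The inconsistency is real and confined to secondary outcome v). An average or median duration is not a valid comparison for times cut off at 1 year unless event-free patients are given a stated rule, and no rule or order of precedence is written.

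The harm is conditional. If event-free patients are left out, the average shows about 23-37% of the true difference in exacerbation-free days for placebo event rates of 50-80% and hazard ratios of 0.5 to 0.8. These rates, the hazard ratios and the exponential shape are assumptions. A reader might take that fraction to apply to any real difference, but it depends on the event rate: about 21% at a 38% rate, up to 58% at 95%.

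Nor is there a basis for inferring spurious positive findings or a threat to the trial's main conclusion. Type I error stays near 5%, and the primary test and N = 84 do not change. Even log-rank has only about 50% power or less at a hazard ratio of 0.6 for event rates of 50-80%, so on those assumptions the outcome is supportive. This is a minor correction, best made before the data are seen.

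**What to change.** In Section E v), replace the average/median sentence with: *Time to subsequent PEx will be shown by Kaplan-Meier curves and compared with the Cox model of Section G; patients with no new PEx are censored at 1 year after the last day of IV therapy of the randomized exacerbation, or at last contact or death if earlier.* Start the 1-year follow-up in the same paragraph from that date.

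In Section G, add that the complete-case rule does not remove event-free patients, and that the final analysis of this outcome follows completion of 1-year follow-up.

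Optional: use the same censored method for the Appendix 1.2 report to the DSMB, and add a sensitivity analysis timed from randomisation, because the last IV day falls after randomisation. The effect of that choice of start date was not calculated here.

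The cost is protocol and SAP wording. IV start and stop dates and the year of follow-up are already planned, so no extra patients, visits or samples are needed.

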Randomization (1:1) will be done through central allocation of a block-randomization schedule prepared through a computer-generated random listing. Randomization will be done by the study data analyst at the Hospital for Sick Children. The analyst will be the only member of the investigative team aware of the randomization assignment and will not be directly doing the statistical analysis. He/she will not be involved in the care of the study patients or the measurement of outcomes in the study. No other research staff nor patients nor physicians will be aware of the randomization assignment. The pharmacist at each study site will call the analyst for randomization.

Once the patient is randomized, the analyst will inform the research pharmacy at each study site and they will distribute either prednisone or placebo (lactose, packaged in #0 capsules of identical appearance) to the hospital ward or the CF clinic according to dosing Table 1. Physicians and patients will be blinded to the treatment, and placebo will be produced to look identical to the treatment drug. The microbiology lab and pulmonary function lab will also be blinded to the treatment allocation. Compliance will be measured by nurses for hospitalized patients and by asking patients to return any unused medication for patients receiving homecare IV antibiotics.

Safety monitoring

Patients who are most at risk of developing side effects secondary to corticosteroid use will be excluded based on the above exclusion criteria. Subjects will be monitored with measurements of urine glucose on day 7, day 10 (\pm 2 days) and on day 14 of antibiotic treatment while on prednisone (or placebo). If the urine glucose is $> 2+$, a serum glucose measurement will be performed. All the information will be provided to the treating physicians; they can decide at any time to withdraw their patient and request unblinding of the treatment allocation. The study will be monitored by a Data Safety Monitoring Board (DSMB) (Appendix 1.2-Data Safety Monitoring Plan).

E. Study outcomes:

Primary outcome:

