pulmonary function data points were available (n=228), we determined that 50% of patients will recover >90% of their baseline FEV₁ at day 7 of antibiotic treatment, with the remaining 50% available for randomization to either prednisone or placebo treatment. Of the 50% who do not recover >90% of baseline FEV₁ at day 7, 30% of these will go on to recover FEV₁ at day 14 of antibiotic treatment. We therefore estimated a 30% placebo response rate. Using these estimates, we calculated the sample size (**power two proportions** command in Stata 13.1) for the comparison of two proportions (Table 3).

For this study, we are aiming for a clinically significant treatment effect size of approximately two and a half-fold (30% response in the placebo arm vs 60% in the treatment arm). In order to have 80% power (at a significance level of 5%) we would need a sample size of **84 (42/arm)**. Estimating a 50% participation rate and a 20% drop out rate, we will need to approach 210 patients.

Since 50% of all patients who present with a PEx recover their lung function by day 7 of antibiotic therapy, 30% of patients will not experience more than a 10% relative drop in FEV₁ (inclusion criteria) and 10% of CF patients have diabetes and are on insulin which is an exclusion criteria (CPDR 2012 and personal communication-CF clinic directors), we will need to screen approximately 650 exacerbation events to approach 210 patients and enroll 105 patients into the study (Table 3). Over the 3 year study period, we expect to enroll enough study participants from all study sites) which will give us a sufficient population from which to enroll our necessary study sample size. We have had face to face meetings and discussions with our team of co-investigators who have been involved in the design and are fully committed to participating in this study. We have successfully collaborated with this team of researchers in previous clinical trials (10, 51) and fully expect we will achieve our current stated aims.

G. Statistical analyses

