If when the statistician estimates the treatment effect between the two groups (above), there is NOT a statistically significant treatment effect ($p>0.05$), the statistician will re-calculate the sample size based on the observed data from 84 participants, in order to determine what sample size is required to observe a statistically significant effect. This data will be provided to the DSMB who will decide whether or not to continue the study, based on feasibility and the clinical relevance of the treatment effect size. Appendix 1.1 includes detailed plans for the analysis of the extension study, which will be designed as an adaptive trial (52).

H. Potential Challenges and Alternative Approaches

The main challenge of this study is the large estimated treatment effect size. The future adaptive trial design, however, allows us the flexibility to calculate the necessary sample size based on observed data if the difference between groups is clinically but not statistically significant. These data will inform the decision whether to continue the trial with the addition of other centers in either Canada or the United States (Deliverables and Future Directions). Another challenge is the number of potential confounders influencing lung function recovery. We have designed this trial to be pragmatic, that is, reflective of real life conditions, as it is not possible to stratify based on all the variables that could affect response such as concomitant medications, hospital vs home IV therapy, choice and duration of antibiotic therapy. Therefore, we will collect all this information and sensitivity analyses will be done to determine whether these variables affect the results.

I. Personnel Requirements and Study Timeline:

We will require a research coordinator at each site over the study period (see Budget).

J. Knowledge Translation (KT):

We have developed a KT plan with the assistance of [name], scientific director of KT at the Hospital for Sick Children (Appendix). Our target audiences for the results of this study are CF clinicians, patients and researchers. We will partner with CF Canada to implement the following KT strategies for disseminating our results: publishing in an open-access journal for all audiences, presenting at national (Canadian Clinics conference) and international CF

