The conduct of the study will be monitored by an independent Data Safety Monitoring Board. We will appoint members, including CF physicians, from Canadian CF centers that are not participating in this trial. In addition, we will also appoint an independent statistician (not involved in this trial) to be on the DSMB. The DSMD will review safety reports on a semi-annual basis, or pre their requested frequency. Under the direction of the statistician on the DSMB, an interim analysis will be performed at the mid-way point of the trial (when 42 patients have been randomized (minimum 21 in each arm) and the primary outcome has been collected) to assess for safety. The DSMB can request unblinding of the data at any time. Serious adverse events will be reported to the DSMB by the PI within 48 hours of their occurrence. In addition,

all serious and unanticipated adverse events will be reported to the local REB as well as the REB at the Hospital for Sick Children with 48 hours of their occurrence, as stated above.

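### 84 is the number left after dropout in Section F but half-counted as randomised in Appendix 1.2, and the decision analysis does not say which is meant; at 84 randomised, power is about 70%, not 80%

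*Combined protocol and SAP*

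**What the plan says.** **Sample size (Section F).** The design effect is "30% response in the placebo arm vs 60% in the treatment arm". The text continues: "In order to have 80% power (at a significance level of 5%) we would need a sample size of" 84, or 42 per arm. It then says: "Estimating a 50% participation rate and a 20% drop out rate, we will need to approach 210 patients". The next paragraph gives the number to enrol as 105. In this section 84 is therefore what remains of 105 after dropout.

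**Analysis rules (Section G).** The primary comparison is a two-sample test of proportions among randomised patients, by intention to treat. The plan adds: "All outcomes will be obtained for all subjects irrespective of whether they completed the study per protocol". The following sentence says that missing data will be handled by complete-case analysis.

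**Decision point (Section G and Appendix 1.1).** Treatment groups are separated and the primary outcome is tested when the target sample size is reached. Neither place gives that target as 84 or 105, or says whether it counts randomised or measured patients. If p is not below 0.05, the sample size is recalculated "based on the observed data from 84 participants" and the DSMB decides whether to extend.

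**Mid-way look (Appendix 1.2, Safety Reviews).** "an interim analysis will be performed at the mid-way point of the trial (when 42 patients have been randomized", with at least 21 per arm and the primary outcome collected. The purpose given is safety.

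**The concern.** If mid-way is 42 randomised, the whole trial is 84 randomised. In Section F the whole trial is 105, of whom 84 are expected to be analysable. Both can be true only if no randomised patient lacks the day-14 outcome. The figure of 105 appears in Section F and nowhere else, so a statistician working from Section G and the appendices could reasonably run the decision analysis at 84 randomised.

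That analysis determines whether the trial is reported as positive or goes to re-estimation and a DSMB decision on extension. If it is run on fewer patients than the power statement assumes, a true effect of the planned size is missed more often than stated. The re-estimation also starts from less data than intended.

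**Working it through.** **Inputs.** Response 30% v 60%, alpha 5%, power 80%, dropout 20%, participation 50% (Section F); 1:1 allocation (Section D); two-sample test of proportions with complete-case handling of missing data (Section G). Sidedness is not stated. Two-sided is assumed because it reproduces all four rows of Table 3 (163, 93, 61 and 42 per arm); a one-sided test would give 33 per arm in the last row.

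**Formula.** With n per arm, d = p2 − p1 and p the mean of p1 and p2:

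power = Φ{ [d√n − 1.96√(2p(1−p))] / √(p1(1−p1) + p2(1−p2)) }

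**1. The plan's own figure.** p = 0.45, so √(2 × 0.45 × 0.55) = 0.7036. √(0.21 + 0.24) = 0.6708.
- n = 42: (0.30 × 6.481 − 1.379) / 0.6708 = 0.843; power 80.0%.
- Inflation: 84 / 0.80 = 105, and 105 / 0.50 = 210.

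All of Section F's figures from 42 per arm to 210 approached reproduce.

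**2. 105 randomised, 20% unmeasured, complete-case.** 105 × 0.80 = 84 analysed, 42 per arm; power 80.0%. The stated power holds on this reading.

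**3. 84 randomised, 20% unmeasured, complete-case.** 84 × 0.80 = 67.2 analysed, 33.6 per arm.
- (0.30 × 5.797 − 1.379) / 0.6708 = 0.537; power 70.4%.
- Enumerating the binomial outcomes for the same test gives 70.3% at 33 and 34 per arm and 70.4% at 34 per arm. The result does not depend on the normal approximation.

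The chance of missing a true 30% v 60% effect rises from 20.0% to 100 − 70.4 = 29.6%.

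**4. Sensitivity: 105 randomised (52 per arm), everyone measured, 20% stop study drug.** The placebo arm stays at 30%. The response of patients who stop is an assumption; the documents do not give it.

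| Patients who stop prednisone | Prednisone-arm response | Power |
|---|---|---|
| Respond like placebo (30%) | 0.8 × 60 + 0.2 × 30 = 54% | 70% |
| Keep half the benefit (45%) | 0.8 × 60 + 0.2 × 45 = 57% | 80% |
| Keep all the benefit (60%) | 60% | 88% |

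**The case against.** **One definition may run throughout.** Appendix 1.2 also requires the primary outcome to have been collected, and the Section G re-estimation refers to observed data. Both could be read as counts of measured patients, which would agree with Section F. This has some force: the wording is loose rather than flatly contradictory. But the count in Appendix 1.2 is of randomised patients, and it is called mid-way. If 105 were the randomised total, mid-way would fall at 52 or 53.

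**Dropout may precede randomisation.** Section F says enrol, not randomise; consent is at day 0 and randomisation at day 7. If all the dropout fell in between, 84 randomised would be consistent, but nothing would then be allowed for missing day-14 results, which Section G expects could occur. Section F also removes the 50% who recover by day 7 before arriving at 210, so its 105 are most naturally patients available for randomisation. The plan does not settle this.

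**A stronger reading is tempting.** A reader might infer that the 80% fails outright, because intention to treat keeps in patients who stop drug and so dilutes the effect to about 70% power. The documents do not support that. Section F inflates for dropout correctly, and with Section G's complete-case rule 105 randomised gives exactly 80.0%. The plan does not equate dropout with stopping drug, and does not confine the 60% to patients who complete treatment. The 70% in step 4 is the low end of a range that reaches 88%.

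**A non-significant result does not end the trial.** This is correct. It leads to re-estimation and a DSMB decision, which softens the consequence of lower power but does not remove it.

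**Conclusion.** The concern holds as an inconsistency in a number on which the trial's main decision depends, not as an arithmetic error. The 80% power belongs to 84 patients with a day-14 outcome and the full 30% v 60% effect. If the decision analysis is triggered at 84 randomised, as Appendix 1.2 implies, about 67 patients are analysed and power is about 70%. This rests on the plan's own 20% dropout falling after randomisation, equally in both arms, with no day-14 value, and on a two-sided 5% test. The point should be corrected before the trigger is applied.

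**What to change.** - **Sections F and G and Appendix 1.1:** define the target once, as 84 randomised patients with a day-14 FEV1, and say that about 105 randomised are expected to be needed. Run the decision analysis and the re-estimation at that point, on all randomised patients with data.
- **Section F:** say whether dropout means a missing day-14 result, stopping study drug, or leaving before randomisation. State that the 80% assumes the full 30% v 60% effect among analysed patients. Give the step 4 values (70%, 80%, 88%) as a sensitivity range, with their assumptions, and not as the expected power.
- **Section G:** say how patients who drop out enter the intention-to-treat comparison alongside the complete-case rule.
- **Appendix 1.2:** describe the look in matching terms, for example as 42 patients with the day-14 outcome. The safety review need not be delayed: if it is to stay at 42 randomised, keep that count and drop the mid-way description.

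The cost is wording in those four places and a more conditional power statement. No patients are needed beyond the 105 already planned.
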